## **6. Measurement of Effect**

This proposal uses the Reach, Effectiveness, Adoption, Implementation, and Maintenance (RE-AIM) model as an organizing evaluation framework to examine the quality, speed, and impact of implementing the adaptive system consultation strategies. RE-AIM is a comprehensive evaluation framework that assesses implementation in five dimensions. While RE-AIM has been used to evaluate many diseases of fidelity. Specific measures for each RE-AIM dimension are presented in Table 1.

## **7. Study Parameters**

**Table 1 Outcome measure by RE-AIM category**

Domain	Source	Pertains to aim:	Months* collected
Reach: # and % of patients excluded vs. participating (incl. characteristics)	EHR	PA, SA1	1-21
Effectiveness: Overall rate of opioid prescribing and average MME per clinic and provider	EHR	PA	1-21
# and % of patients completing urine drug testing (past 12 mo.)	EHR	PA	1-21
# and % of patients screened for mental health using PHQ-2 (past 12 mo.)	EHR	PA	1-21
Mental health (PHQ-9) scores for patients screening positive on PHQ-2 (past 12 mo.)	EHR	PA	1-21
Overall rate and dose of opioid-benzodiazepine co-prescribing	EHR	PA	1-21
# and % of patients with treatment agreements (past 12 mo.)	EHR	PA	1-21
# and % of opioid prescriptions above 90 MME	EHR	PA, SA1	1-21
Patient attendance at scheduled clinic visits	EHR	PA, SA2	1-21
# and % of patients prescribed buprenorphine	EHR	PA	1-21
# and % of patients with PEG-3 score (past 12 mo.)	EHR	PA	1-21
PEG-3 scores (past 12 mo.)	EHR	PA	1-21
Adoption (setting): # and % of participating clinics vs. all clinics (incl. characteristics)	HS	SA1	1-21
Adoption (staff): # and % of participating staff vs. all eligible clinic staff (incl. characteristics)	Clinic	SA1	1-21
Clinician attendance at intervention meetings	RT	SA1	1-21
Implementation: Hours of intervention received per clinic & prescriber	RT	SA1	1-21
Adaptations made to protocols during intervention period	RT	SA1	1-21
Assessment of 4 moderators: system-level opioid prescribing policy, clinic-level experience in QI, size of clinic (# patients), # and % of patients on opioid doses > 90 MME	RT; EHR	SA1	0, 5, 9, 21
Qualitative assessment of mechanisms of action & factors influencing implementation	RT	SA1	1-21
Cost of each different implementation sequence & combination	RT	SA2	1-21

Clinics will be randomized on a 1:1 ratio to either receive practice facilitation plus academic detailing or academic detailing alone at month 3. At month 9, all clinics will be randomized on a 1:1 ratio to either continue the current intervention or add physician peer coaching to the bundle of strategies. It is anticipated that up to 152 prescribers will be recruited from 40 primary care clinics among 2 healthcare systems. The intervention will last for 21 months followed by a 6 month follow-up period.

[figure not shown]
## **8. Statistical Considerations**

### **Research Design**

Analyses will be conducted at two levels, (1) at the clinic level and (2) at the prescriber level. UW Health and Bellin Health primary care clinics will be recruited for participation in the intervention and data collection activities. All clinics and all prescribers within clinics, once randomized, will be included in the intent-to-treat sample. The primary research outcome is morphine milligram equivalent (MME) and will be available for all prescribers within all clinics that consent, regardless of intervention engagement or drop-out.

This study will use a sequential, multiple assignment randomized trial (SMART), which is a factorial design (see Figure 1). This SMART has 4 implementation strategies embedded within it.

Figure 2. Study design

**Qual assmnt:** Qualitative assessment  
**EM:** Educational meeting  
**AF:** Audit with monthly feedback reports

**R:** Randomization point  
**PF:** Practice facilitation  
**PPC:** Prescriber peer consulting

## **Quantitative data collection and analysis**

Data are available for many study measures, allowing for time-series analysis of repeated measures to detect changes in a clinic over time (pre-intervention vs. post-intervention). Clinics and prescribers will be compared to clinics and prescribers receiving only academic detailing by accessing measures through the Wisconsin Collaborative Healthcare Quality system-wide data warehouse at Health Innovation Program (HIP). Programmers and compliance officers at HIP will prepare a de-identified dataset analysis purposes by the study statistician. The dataset will remain on HIP's secure data servers at all times.

The quantitative analysis of data from the electronic health record (EHR) will focus primarily on average daily morphine milligram equivalent for chronic pain patients at the clinic and prescriber levels. Changes in outcomes will be assessed through repeated monthly observations assessed retrospectively post-intervention. Data will be collected every three months throughout the 21 month intervention and 6 month follow-up period.

The study team will analyze the de-identified dataset delivered by HIP for evaluation purposes. The research team will not have access to any individual patient data or PHI. Prescriber identities will be protected; identifying information (such as staff names) will be replaced with code numbers by the HIP Programmers. The de-identified dataset will be coded by prescriber and clinic and the code key will be kept by HIP Programmers and not provided to the study team.

Due to delays in the data delivery from the Wisconsin Collaborative Healthcare Quality the research team will also receive and analyze data that the UW Clinical Research Data Services (CRDS) provides for the clinic feedback reports. The purpose for this is to speed up data analysis. CRDS will act as an honest broker and will not provide the research team with patient-level identifiable data. CRDS will provide data to the research team through ICTR REDCap's file repository feature.

## **Qualitative data collection and analysis**

Interviews over WebEx for practice facilitation and physician peer coaching will be recorded and transcribed. Subjects will be reminded that calls are recorded. The recordings will be transcribed and coded by the study team. Qualitative analyses will be done using Nvivo.

Qualitative assessments will be conducted to assess contextual factors of systems consultation. These assessments will be coded to group data at the clinic level for analysis and take place at months 0, 5, 9, and 21 of the intervention.

Qualitative data will be collected via REDCap at the prescriber levels will be stored REDCap for analysis purposes. Any publication that results from the study data will not include the names of clinics or staff members where data were collected. All other results will be presented in anonymous aggregated form.

## **Statistical analysis**

Statistical analysis will be conducted by [name] at the University of Michigan. [name] will be provided a secure, remote login to the password-protected servers at the Health Innovation Program to access the de-identified datasets.

The analysis will use a longitudinal (repeated-measures) analysis. Time will be coded such that  $t=0$  denotes month 3 of the intervention period (the initial randomization); in the following text, data collected prior to  $t=0$  is considered baseline data (including the MME prior to month 3). The primary outcome (MME) is a continuous measure and is collected at  $t=0$  (at month 3, prior to randomization) and every 3 months up to  $t=18$  (intervention month 21) for a total of 7 measurement occasions. (Note that the primary outcome is clustered: repeated measures, within prescribers, within clinics.) Longitudinal regression models, adapted for the analysis of a longitudinal SMART and further extended for use with data arising from a cluster-randomized SMART, will be used to contrast the 4 sequences and combinations of implementation strategies in terms of the average change in MME.

A piecewise-linear model with a knot at  $t=6$  (MME collected immediately before the second randomization at intervention month 9) will be used to model the temporal trajectories over the course of months 10-21. The model the study plans to use has a linear trend from  $t=0$  to  $t=3$  for prescribers in academic detailing plus practice facilitation and academic detailing only clinics, and a linear trend from  $t=3$  to month  $t=18$  for each of the 4 sequences and combinations of implementation strategies. We allow for changes in the mean trajectory (i.e., deflections) at intervention month 9 ( $t=6$ ) since this is the point at which prescribers may begin receiving physician peer coaching.

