### **Primary Aim:**

Compare the effect of an adaptive systems consultation implementation strategy vs. academic detailing alone on average morphine milligram equivalent dose over 21 months.

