## **Randomization**

Randomization will take place at the clinic level at month 3 (practice facilitation) and month 9 (physician peer coaching). A research team member will conduct the randomization using the urn randomization program.

Randomization of clinics will take place at intervention month 3 on a 1:1 ratio to assign clinics that will receive practice facilitation plus academic detailing or academic detailing only. At intervention month 9 all clinics will be randomized on a 1:1 ratio to assign clinics who will receive the current intervention strategy plus physician peer coaching or continue the current intervention strategy for 12 months. Randomizations will be stratified on clinic's 1) health system, 2) number of patients, and 3) average MME being greater or equal to the health system's clinic average.

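### The primary model's slope sentence splits the four sequences at t=3 (month 6), but the stated knot and the second randomization are at t=6 (month 9)

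*Combined protocol and SAP*

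**What the plan says.** Section 8, Statistical analysis, codes time so that t=0 "denotes month 3 of the intervention period (the initial randomization"). Measurements follow every three months to t=18, which is month 21, giving seven occasions. Three consecutive sentences then describe the mean model for the primary outcome:

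1. The knot: "A piecewise-linear model with a knot at $t=6$ (MME collected immediately before the second randomization at intervention month 9").
2. The slopes: a linear trend over t=0 to t=3 for the two first-stage arms, then "a linear trend from $t=3$ to month $t=18$ for each of the 4 sequences and combinations of implementation strategies".
3. The deflection: the model allows "changes in the mean trajectory (i.e., deflections) at intervention month 9", given there as t=6, "since this is the point at which prescribers may begin receiving physician peer coaching".

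The design sections agree on when coaching is assigned. Section 4, Randomization: "Randomization will take place at the clinic level at month 3 (practice facilitation) and month 9 (physician peer coaching"). Section 7, Study Parameters: "At month 9, all clinics will be randomized on a 1:1 ratio to either continue the current intervention or add physician peer coaching".

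**The concern.** The second sentence cannot stand beside the first and third. A single straight line from t=3 to t=18 has no bend at t=6. The sentence also divides two groups into four at month 6, three months before the randomization that creates the four groups.

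It is the only sentence that says which groups have which slopes over which interval, and the documents give no model equation. An analyst who follows it would let the coached and uncoached clinics differ at the month 9 measurement, which the plan says is taken before coaching is assigned. If coaching works, part of its effect would be placed before it began and its monthly slope would be understated. A choice between the two readings made after the data are seen would also invite the question whether the outcome guided it.

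**Working it through.** **Time coding.** t = month − 3. Occasions t = 0, 3, 6, 9, 12, 15, 18 are months 3, 6, 9, 12, 15, 18, 21. That is seven occasions, as the plan states. Month 9 is 9 − 3 = 6, which reproduces the stated knot. t=3 is month 6.

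**Distinct group means implied by each version**

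| Occasion | Fork at t=6 | Fork at t=3 |
|---|---|---|
| t=3 (month 6) | 2 | 2 |
| t=6 (month 9, before second randomization) | 2 | 4 |
| t=9 (month 12) | 4 | 4 |

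Only the fork at t=6 matches the design.

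**Other readings.** Taking t as an occasion number fails, because the sentence runs to t=18 and there are seven occasions. Taking t=3 to mean intervention month 3 fails, because that is t=0. Two knots, at t=3 and t=6, fail because one knot is named and t=3 to t=18 is described as one linear trend.

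**Size if coded literally.** The documents give no expected trajectories, so the true effects here are assumptions. Noise-free means for the four sequences were projected by generalised least squares onto the t=3 fork. Four working correlations were used: independent, exchangeable 0.5, exchangeable 0.7, and AR(1) 0.8 between adjacent occasions.

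*Scenario A: coaching lowers MME by 1.5 per month from t=6, so by 18 at t=18.* The independent case can be done by hand. The fitted coaching contrast is θx with x = max(t − 3, 0) = 0, 0, 3, 6, 9, 12, 15. The true contrast is y = −1.5 × (0, 0, 0, 3, 6, 9, 12).

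- θ = Σxy / Σx² = −1.5 × (6×3 + 9×6 + 12×9 + 15×12) / (9 + 36 + 81 + 144 + 225) = −1.5 × 360/495 = −1.091 per month.
- At t=6: 3 × (−1.091) = −3.27 (truth 0).
- At t=18: 15 × (−1.091) = −16.36 (truth −18).
- Average over t=0 to 18: ½ × 15 × (−16.36) / 18 = −6.82. Truth: ½ × 12 × (−18) / 18 = −6.0.

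*Scenario B: facilitation lowers MME by 9 by t=6 and then levels off, with no coaching effect.*

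*A and B together: the contrast of all three strategies with detailing alone, which the Power section uses for sample size.*

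Reductions in MME across the four working correlations:

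| Quantity | Truth | t=3 fork | Error |
|---|---|---|---|
| A, coaching slope per month | 1.5 | 1.09 to 1.20 | −27% to −20% |
| A, difference at t=6 | 0 | 3.3 to 3.6 | – |
| A, difference at t=18 | 18 | 16.4 to 18.0 | −9% to 0% |
| A, average over t=0–18 | 6.0 | 6.8 to 7.5 | +14% to +25% |
| B, difference at t=6 | 9 | 5.7 to 7.3 | −37% to −19% |
| B, difference at t=18 | 9 | 9.4 to 9.9 | +5% to +10% |
| B, average over t=0–18 | 7.5 | 6.3 to 7.4 | −16% to −1% |
| A+B, difference at t=18 | 27 | 26.2 to 27.9 | −3% to +3% |
| A+B, average over t=0–18 | 13.5 | 13.7 to 14.9 | +1% to +11% |

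**Where there is no bias.** A null coaching effect gives a coaching contrast of exactly 0 at t=6 and t=18. A constant facilitation effect of −1 per month with no coaching effect is recovered exactly (−6 at t=6, −18 at t=18). The t=6 fork, and a t=3 fork with an added t=6 deflection, recover the true means in every scenario (error below 1e-12).

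**The case against.** The section largely corrects itself. It names one knot, ties it to the second randomization, says the model is for months 10 to 21, and repeats t=6 with a reason. Only one reading fits the design, and a designated analyst using SMART-specific longitudinal methods would very probably choose it. Harm requires following one sentence and ignoring its neighbours, and fitting the t=6 deflection that the plan also mentions removes the bias.

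The illustration can also be called generous. Scenario A gives coaching alone 18 MME, the difference the Power section calls detectable for the whole three-strategy package. The errors scale with the effect: at 9 MME the false t=6 difference is 1.6 to 1.8. The direction depends on the estimand too. The coaching slope is understated, but its average over time is overstated, and the average is arguably closer to the primary aim, the effect of the adaptive strategy against "academic detailing alone on average morphine milligram equivalent dose over 21 months".

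All of this stands, and it limits the severity. It does not remove the contradiction. No other passage corrects the sentence, and one straight line from t=3 to t=18 leaves no room for the deflection. The text therefore cannot be followed in full, and someone has to decide which part to drop.

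**Conclusion.** The point holds: the slope sentence of the primary outcome model is wrong as written. The contradiction follows from the plan's own time coding and the month 9 randomization, and rests on no assumption about effects. A drafting slip is the likely cause.

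The numerical consequence is modest. It depends on literal coding without a t=6 deflection and on the assumed trajectories. The contrast used for sample size is the least affected at the end of the study; stage-specific coaching and facilitation effects are affected more. No false coaching effect was produced when coaching did nothing. This should be fixed because it is the primary model, but it does not threaten the design.

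**What to change.** In the slope sentence of Section 8, Statistical analysis, change both t=3 entries to t=6. The model then has one slope per first-stage arm from t=0 to t=6 and four sequence-specific slopes from t=6 to t=18. This matches the stated knot, the stated deflection and the second randomization.

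The cost is two edits in one sentence, with no new data and no change to the design. The correction should be dated before the outcome data are analysed, so that the position of the knot cannot be read as a choice made after seeing results.

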## **Cost analysis**

This study will estimate the cost of delivering the four different sequences and combinations of strategies, including incremental cost effectiveness of adding practice facilitation and physician peer coaching. Methods and instruments used for cost data collection in the Systems Consultation R34 will be used. Detailed logs of call contacts between members of the research team and the clinic change teams will be kept to estimate the number of hours spent delivering the implementation strategy. The consultants will document the date and duration of each contact they have with clinic staff members, role of the staff member, and a summary of topics discussed. Cost estimates of the intervention will be calculated by multiplying hourly wage rates for physician peer coaches and practice facilitators. Costs for non-personnel may include travel to site visits, the cost of teleconferencing services for follow-up calls, etc.

## **Power**

The estimated sample size for this study is based on the primary aim: a comparison on change in morphine milligram equivalent (MME) between implementation sequences of all three strategies vs. academic detailing only. Based on the pilot data, the inter-clinic correlation coefficient was 0.14. Assuming the average prescribers per clinic is 4, a type-1 error rate of 5%, and an early adoption rate of 50% gives a total of 40 primary care clinics at 80% power to detect an effect size of  $d=0.66$  between the two implementation sequences on change in MME. In the pilot data we found a standard deviation of 35 MME, which is estimated to detect differences on MME as small as 18 MME.

Data to be collected	Storage	Type of Data
Clinician subject intake	REDCap/ Locked cabinet	Coded
Clinician subject demographics	REDCap/ Locked cabinet	Coded
Qualitative assessment data	REDCap/ Locked cabinet	Coded
Prescriber consent form	REDCap/ Locked cabinet	Coded
Systems consultation coaching log	Box folder/ Locked cabinet	Coded
De-identified patient electronic health record data	HIP	De-identified
Practice facilitation notes	Box folder	Coded
Audio recordings from PF/PPC sessions	Facilitator computer/laptop (audio) or WebEx cloud storage (video)	Recording
Audio recordings from interviews	WebEx secure cloud storage	Recording
Transcriptions of interviews	Box folder	De-identified
Physician peer consulting survey	UW Qualtrics	Coded

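### The power statement relies on an undefined 50% early adoption rate, whose most plausible reading does not fit a design that re-randomizes every clinic, so the stated 80% cannot be matched to the written plan

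*Combined protocol and SAP*

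**What the plan says.** Section 8, Power, sizes the trial on "a comparison on change in morphine milligram equivalent (MME) between implementation sequences of all three strategies vs. academic detailing only". The inputs are an intraclass correlation of 0.14 from the pilot, an average of 4 prescribers per clinic, a 5% type-1 error rate with no sidedness given, and a 50% early adoption rate. The result is worded as "an early adoption rate of 50% gives a total of 40 primary care clinics at 80% power to detect an effect size of" d=0.66. The paragraph then gives a pilot SD of 35 MME and a detectable difference of 18 MME.

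The second randomization is described twice. Section 4, Randomization: "At intervention month 9 all clinics will be randomized on a 1:1 ratio". Section 7, Study Parameters, below Table 1: "At month 9, all clinics will be randomized on a 1:1 ratio to either continue the current intervention or add physician peer coaching". Section 8, Research Design, adds "This study will use a sequential, multiple assignment randomized trial (SMART), which is a factorial design" and "This SMART has 4 implementation strategies embedded within it". The same text below Table 1 gives the planned numbers: "It is anticipated that up to 152 prescribers will be recruited from 40 primary care clinics among 2 healthcare systems".

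The planned analysis (Section 8, Statistical analysis) is a seven-occasion piecewise-linear longitudinal model that "will be used to contrast the 4 sequences and combinations of implementation strategies in terms of the average change in MME".

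**The concern.** The early adoption rate is one of the inputs said to produce the 40 clinics, yet the text never says what an early adopter is. Elsewhere adoption is a RE-AIM evaluation domain, measured by participation and contact logs, and not a clinic status at month 9 that decides who is randomized again. In a SMART, a rate of this kind most naturally describes clinics that are spared the second randomization. Such clinics count toward both second-stage options, which reduces the number needed. The written design has no such group.

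This is the only sample-size justification, and it concerns the primary aim. If the calculation borrowed precision from an exempt group that does not exist, the chance of missing a true effect of d=0.66 is larger than the 20% stated, and a null result would be read with too much confidence.

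**Working it through.** **Inputs.** From Power: ICC 0.14, m=4 prescribers per clinic, alpha 5%, N=40 clinics, power 80%, d=0.66. From Study Parameters: 152/40 = 3.8 prescribers per clinic, used as a sensitivity value. Assumptions: the formula below and, unless noted, a two-sided test.

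**Formula.** In units of the prescriber-level SD, the variance of a clinic mean is v = [1+(m-1) x 0.14]/m. This is 1.42/4 = 0.355 at m=4 and 1.392/3.8 = 0.366 at m=3.8. Let p be the share of clinics not re-randomized. Inverse-probability weights are 2 for those clinics and 4 for the rest. The two sequences compared start with different first-stage options, so they share no clinics, and the contrast variance is 2 x [2p + 4(1-p)] x v / N. Power (normal) is Phi(0.66/SE - 1.96). The N for 80% is 2 x [2p + 4(1-p)] x v x (1.96+0.842)^2 / 0.66^2.

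**Reproducing the stated figure, p=0.5.**
- m=4: SE = sqrt(6 x 0.355/40) = 0.2308; power 81.6%; N = 38.4.
- m=3.8: SE = sqrt(6 x 0.366/40) = 0.2344; power 80.4%; N = 39.6; detectable d = 2.802 x 0.2344 = 0.657.

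These agree closely with 40 clinics, 80% and d=0.66. The p that gives exactly 80% at N=40 is 0.44 (m=4) or 0.48 (m=3.8).

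**The design as written, p=0 (about 10 clinics per sequence).**
- m=4: SE = sqrt(8 x 0.355/40) = 0.2665; 0.66/0.2665 = 2.477; power = Phi(0.517) = 69.7%. N for 80% is 51.2. Detectable d = 2.802 x 0.2665 = 0.75.
- m=3.8: SE 0.2707; power 68.4%.

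| Two-sided, p=0, m=4 | Power at d=0.66 | Detectable d at 80% |
|---|---|---|
| Normal | 69.7% | 0.75 |
| t, 36 df (variance pooled over four sequences) | 67.4% | 0.77 |
| t, 18 df (two sequences only) | 64.9% | 0.79 |

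**One-sided 5%, p=0, m=4.** Phi(2.477 - 1.645) = 79.7%, N = 40.3; by t, 78.4% (36 df) or 77.0% (18 df).

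**Planned longitudinal model.** This check takes the month-21 minus month-3 contrast with all clinics re-randomized, 4 prescribers per clinic, a common mean at t=0, the knot at t=3 or t=6, ICC 0.14 throughout and d scaled to the SD of change. The covariances are assumed. Two-sided normal power:
- Covariance fully used: 88-97% under compound symmetry (correlation 0.3-0.9), 77-90% under AR(1) (0.80-0.97 per 3 months), 79-88% with random slopes, 73-77% under a random walk.
- Working independence with robust variance, compound symmetry: 91-92% at correlation 0.3, 72% at 0.5, 43-44% at 0.7.

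**MME difference.** 0.66 x 35 = 23.1, whereas 18/35 = 0.51. The stated d, SD and MME difference do not agree if d refers to the SD of 35.

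**The case against.** The strongest reply is that nothing in the text says an early adopter escapes the second randomization. That meaning comes from solving backwards with a formula the plan does not print, and the design figure is not in the text available here. The match is also not unique. A one-sided 5% test with every clinic re-randomized gives 79.7% at the stated 4 prescribers per clinic, closer to 80% than the 81.6% from the exempt-group reading. This stands, and it is why the conflict is put as an inference. The one-sided reading, however, gives the listed 50% nothing to do, and no one-sided test is stated. If the figure does show an exempt group, it would have to be reconciled with the two statements that all clinics are randomized again.

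The second reply is that 70% describes a comparison of clinic means, while the plan specifies a longitudinal model. This also stands. A reader might infer that the trial's true power is 70%, or that the 80% has been shown to be wrong. The documents support neither: with every clinic re-randomized, many plausible covariances put the planned model above 80%, and others put it well below.

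It can be added that the plan's figures hint at a correlation. If 35 is a single-occasion SD (an assumption), 18/0.66 gives a change SD of 27.3 and a correlation of 1 - (27.3/35)^2/2 = 0.70. Under compound symmetry that gives 91-93% with the covariance fully used but 43-44% with working independence. The hint therefore does not settle the matter, and the Power paragraph claims no longitudinal gain.

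**Conclusion.** The concern holds in a limited form. The Power paragraph depends on an input that is undefined, and the reading that uses every listed input and returns about 40 clinics and 80% needs a group that the written design does not contain. The stated 80% is therefore not shown to apply to the design as written.

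If the 80% was meant for a two-sided comparison of clinic means, the corresponding figure is about 70% (65-67% by t). An effect of d=0.66 would then be missed about 30% of the time rather than 20%. That size rests on the inferred formula, two-sidedness, equal allocation and no gain from repeated measures. It is not an estimate of the planned model's power, which the documents leave undetermined. Confidence is medium, because the role of the 50% is inferred; that the term is undefined and the sidedness unstated is plain from the text.

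**What to change.** In Section 8, Power:

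1. Delete the early adoption term, or define it and reconcile it with Randomization, Study Parameters and Research Design.
2. State the sidedness, the analysis assumed for power, and the SD to which d refers.
3. Restate power at d=0.66, or the detectable d at 80%, for 40 clinics all re-randomized under that method. For a two-sided clinic-mean comparison this is about 70%, or d of about 0.75 (normal). If the method is the longitudinal model, give the assumed within-prescriber correlation and working covariance. If a one-sided test was intended, say so.
4. Recompute the MME difference from the same d and SD.

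The cost is one paragraph of wording and possibly a less favourable stated power. The number of clinics, the randomization and the analysis do not change.

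### The detectable difference of 18 MME does not follow from d = 0.66 and an SD of 35 MME, which together give 23.1 MME

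*Combined protocol and SAP*

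**What the plan says.** Everything needed is in section 8, Power, of the combined protocol and SAP. The comparison is between the sequence with all three strategies and academic detailing alone. The paragraph assumes 4 prescribers per clinic and a 5% type I error, and reports from the pilot that "the inter-clinic correlation coefficient was 0.14". It then says that "an early adoption rate of 50% gives a total of 40 primary care clinics at 80% power to detect an effect size of" d = 0.66 "between the two implementation sequences on change in MME". The next sentence moves to MME units: the pilot showed "a standard deviation of 35 MME, which is estimated to detect differences on MME as small as 18 MME".

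The SD of 35 is not labelled as the SD of a single measurement, of a change, or of a model residual. Section 8, Statistical analysis, contrasts the sequences "in terms of the average change in MME" and collects the outcome "for a total of 7 measurement occasions", but gives no correlation between occasions and no SD of change.

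**The concern.** The sentence reads as though 18 MME is what d = 0.66 amounts to when the SD is 35. A standardised effect times its SD should return the raw difference, and here it does not.

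The 18 MME figure is the plan's only statement, in the outcome's own units, of what the trial can detect for its primary aim. A reader weighing a null result, or asking whether the target is clinically sensible, would use it. If 35 is the SD behind d, the figure makes the trial look more sensitive than it is.

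**Working it through.** **Inputs.** From Power: type I error 5% (sidedness not stated), power 80%, d = 0.66, ICC 0.14, m = 4 prescribers per clinic, early adoption 50%, 40 clinics, SD 35 MME, stated difference 18 MME. From section 2: 152 prescribers in 40 clinics, so m = 152/40 = 3.8 as an alternative. From section 4, Randomization: "At intervention month 9 all clinics will be randomized on a 1:1 ratio".

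**Step 1. Reproduce the plan's 40 clinics.** With normal quantiles,

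N = 4 (z_α + z_β)² × [1 + (m − 1) ICC] × f / (m d²).

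The plan gives no formula, so the variance factor f for comparing two embedded sequences is an assumption: 1.5 if the 50% early adopters are not re-randomised, 2 if all clinics are, 1 for a plain two-group comparison.

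- Two-sided, f = 1.5, m = 4: 4 × 7.849 × 1.42 × 1.5 / (4 × 0.4356) = 38.4 clinics; power with 40 clinics 81.6%.
- Two-sided, f = 1.5, m = 3.8: 39.6 clinics; power 80.4%.
- One-sided, f = 2, m = 4: 40.3 clinics; power 79.7%.

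So 40 clinics for d = 0.66 can be reproduced. The difficulty is in the conversion to MME.

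**Step 2. Convert d to MME.**

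- 0.66 × 35 = 23.1 MME.
- Rounding limits: 0.655 × 34.5 = 22.6 and 0.665 × 35.5 = 23.6, so rounding does not explain 18.
- In reverse: 18 / 35 = 0.514, and 18 / 0.66 = 27.3 MME for the SD that would be needed.
- Shortfall: 1 − 18/23.1 = 22%.

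**Step 3. Try the one correlation that is given.**

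- Within-clinic SD: 23.1 × √(1 − 0.14) = 21.4 MME.
- Dividing by the root design effect: 23.1 / √1.42 = 19.4 MME.

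Neither gives 18.

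**Step 4. Find what unstated input would give 18.** Suppose 35 is the SD at one time point and r is an assumed within-prescriber correlation over time. The detectable difference is 23.1 × √(2(1 − r)) for a simple change score and 23.1 × √(1 − r²) with baseline adjustment.

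| Assumed r | Change score (MME) | Baseline-adjusted (MME) |
|---|---|---|
| 0.5 | 23.1 | 20.0 |
| 0.6 | 20.7 | 18.5 |
| 0.7 | 17.9 | 16.5 |
| 0.8 | 14.6 | 13.9 |

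A result between 17.5 and 18.5 needs r of about 0.68 to 0.71 for a change score, or 0.60 to 0.65 with baseline adjustment.

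**Step 5. Try a different comparison.** With f = 1 (all 40 clinics in two groups, m = 4, two-sided), 80% power is reached at d = 0.528, and 0.528 × 35 = 18.5 MME. That is close to 18, but it is neither the stated d nor the comparison of two sequences that the paragraph describes.

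**Step 6. Power for a true difference of 18 MME if 35 is the SD behind d.** Accepting the stated 80% at d = 0.66:

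- Two-sided: Φ(2.802 × 18/23.1 − 1.960) = 0.588.
- One-sided: Φ(2.486 × 18/23.1 − 1.645) = 0.615.

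From the design inputs instead (40 clinics, m = 4): 61% two-sided with f = 1.5, 61% one-sided with f = 2, and 49% two-sided with f = 2. In the last case power at d = 0.66 is itself only 70%.

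**The case against.** The best reply is that d is defined on change in MME, while 35 is not called an SD of change. If 35 is the spread of MME at one time point, multiplying it by 0.66 mixes two scales. A correlation near 0.70 is plausible for repeated prescribing data and would give 17.9 MME. On that view the plan has left out an input but made no arithmetic error, and replacing 18 by 23 could swap a right figure for a wrong one.

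Much of this stands. The documents do not show that 18 is wrong, and the correction has to allow for this explanation. It does not rescue the sentence as written, because the correlation appears nowhere and the result depends heavily on it: from 23.1 down to 14.6 MME for a change score as r goes from 0.5 to 0.8.

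Two smaller replies are also fair. First, the lower power figures under re-randomisation of every clinic (f = 2, two-sided) come from a separate question about the early-adoption assumption; the 18 versus 23 discrepancy does not depend on them. Second, the practical consequence is limited: the clinic count rests on d = 0.66, and no other section uses 18 MME as a threshold.

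**Conclusion.** The concern holds. As written, 18 MME does not follow from d = 0.66 and an SD of 35 MME, and nothing else in the documents reconciles them.

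If 35 is the SD behind d, the detectable difference is 23.1 MME and the stated value is 22% too low. Power for 18 MME is then about 59% (two-sided) or 62% (one-sided), provided the claimed 80% at d = 0.66 is accepted; on other design assumptions it ranges from 49% to 61%. If d was scaled on a smaller SD, 18 may be correct, but it rests on an SD or correlation that the plan does not report. The sample size is not put in doubt by this point.

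**What to change.** Check the pilot calculation and correct the sentence in one of two ways.

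- If the sponsor can document the SD of change or residual SD that was used for d = 0.66, state that SD and its source, label 35 MME as the single-time SD, and give the detectable difference as 0.66 times the documented SD.
- Otherwise, restate the detectable difference as about 23 MME at an SD of 35 MME.

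The cost is one sentence in the Power paragraph. The number of clinics, the randomisation and the analysis stay as they are. The only downside is that the stated detectable difference may become less favourable.
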